7.5.1 Biomarker of Exposure

7.5.1.1 Exhaled CO and Carboxyhemoglobin

Carboxyhemoglobin measured in blood and exhaled CO will be investigated as a measure of exposure to CO in all three study arms. A CO breath test should be conducted in timely conjunction with the blood sampling for COHb, where applicable. In the SA arm, the CO breath test will serve as a verification of compliance. (Section 6.5.4).

CO Breath Test

Carbon monoxide in exhaled breath will be measured using the Smokerlyzer® device such as Micro 4 Smokerlyzer® device or similar in all 3 study arms.

During the confinement period on Days -1 to Day 5, the CO breath test will be conducted four times per day. The first assessment should be conducted within 15 minutes prior to the first product use. The other 3 assessments should be conducted as described in Section 9.

For subjects in the SA arm from Day 1 onwards, the first CO breath test will be done at between 08:00 AM-09:30 AM. The other 3 assessments should be conducted as described in Section 9.

On Day -2 and Day 6, and during the ambulatory period on Day 30 Visit (Day 30), Day 60 Visit (Day 60), and Day 90 Visit (Day 90), the CO breath tests will be conducted once, irrespective of time of product use.

Carboxyhemoglobin

COHb measurement will be performed in all 3 study arms at a local laboratory. Carboxyhemoglobin will be assessed on a daily basis from Day-1 until Day 5.

On Day -1 to Day 4: one blood sample will be collected in the evening between 8:00 PM-09:30 PM.

On Day 5: one blood sample will be collected within 15 minutes prior first product use. The three other blood samples will be collected as described in Section 9.

For subjects in the SA arm from Day 1 onwards, the first COHb will be done between 08:00AM-09:30 AM. The three other blood samples will be collected as described in Section 9.

On Day 30 Visit (Day 30), Day 60 Visit (Day 60) and Day 90 Visit (Day 90): for all study arms, one blood sample will be collected during the visit, irrespective of the time of product use.

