7.7.2 Urine samples

Spot urine samples will be used for the urine drug screen, urine cotinine screen, urine pregnancy test, and safety urinalysis.

24-hour urine collection during the confinement period:

For the 24-hour urine collection, subjects will empty their bladders shortly before 06:30 AM on the study day indicated in the Schedule of Events (Appendix 1). The collection period starts at 06:30 AM and ends on the following day at 06:29 AM. Shortly before 06:29 AM, after nearly 24-hours of urine collection, subjects will empty their bladder again and this urine will be used as the final portion of the 24-hour urine sample.

At time of Discharge on Day 6, subjects will empty their bladder shortly before 06:29. This will be the last urine portion for the 24-hour urine for the Day 5 dot mark in the Schedule of Events.

24-hour urine collection during the ambulatory period:

Twenty four-hour urine fraction will be collected on Day 30 Visit, Day 60 Visit, and Day 90 Visit) at site.

Subject will be asked to come at site at around 08:00 AM on Day 30, Day 60 and Day 90 and will remain overnight on site until respectively Day 31, Day 61, and Day 91. Subject will be asked to empty his bladder on Day 30, Day 60, and Day 90 shortly before 09:00 AM minutes (this urine will be discarded). Then collection period will start at 09:00 AM \pm 20 minutes. After nearly 24-hours of urine collection the day later at 08:59 AM \pm 20 minutes, subjects will empty their bladder again and this urine will be used as the final portion of the 24-hour urine sample.

For both confinement and ambulatory periods;

All urine passed during the sampling period must be collected and put into the sampling bottle, with the exception of about 10 mL for the spot urine tests (described above). No urine

must be passed into the toilet. The volume of 24-hour urine, the start and the end time of urine collection will be recorded by the study collaborators.

For assessment of urine BoExp, creatinine for normalization of urine BoExp, 8-epi-PGF2 α and 11-TBX-B2, sample bio-banking and urine mutagenicity, aliquots from the 24-hour urine collection will be taken. In the Schedule of Events for the 24-hour urine collection (see Appendix 1), the dot corresponds to the day on which the 24-hour urine collection period starts. For example, for NEQ measured at Day 30 Visit in the 24-hour urine collection that starts on Day 30 and ends later on Day 31.

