10:00 AM-11:30 AM		CO breath test	Irrespective of the time of product use
10.00 AM-11:30 AM	✓	COHb in blood	Irrespective of the time of product use
10.00 AM-11:30 AM	✓	Nicotine, cotinine in plasma	One blood sample will be drawn, irrespective of the time of product use

Data and information contained in this document are considered to constitute trade secrets and confidential commercial information, and the legal protections provided to such trade secrets and confidential information are hereby claimed under the provisions of applicable law. No part of this document may be publicly disclosed without the written consent of Philip Morris Products S.A.

Time	Blood sample	Procedures	Additional information
Start of procedure	Day 30 and Day 60		
12:30 PM-01:30 PM		End of HST recording	The HST should be recorded over a period of 4 hours ± 15 minutes. HST recording will be done only on the subject's assigned product
Before 02.30 PM		Lunch	
02:30 PM -07:00 PM		ECG	At least 10 minutes in supine position prior to recording
02:30 PM -07:00 PM		Physical examination, including weight calculated BMI,	
02:30 PM -07:00 PM		Vital signs (blood pressure, pulse rate, respiratory rate)	At least 5 minutes in supine position prior to measurement Systolic and diastolic BP to be evaluated also as risk markers
08:00 PM-09:30 PM		HST questionnaire (THS 2.2 Menthol and mCC arms only)	If compatible mCC are smoked
08:00 PM-11:00 PM		MCEQ questionnaire (THS 2.2 Menthol and mCC arms only), QSU-brief questionnaire	
In the evening before 09:00 PM		Dinner	
11:00 PM		End of Product use	
08:00 AM-11:15 PM		Collection of empty/partially used Menthol Tobacco Stick packs	For accountability Partially used packs will be returned to the subject
08:00 AM-11:15 PM		Collection of tobacco plugs from each used Menthol Tobacco Sticks	For further analysis

Abbreviations: 11-DTX-B2 = 11-dehydro-thromboxane B2; AE = adverse event; BoExps = biomarkers of exposure; CO = carbon monoxide; COHb = carboxyhemoglobin; HDL: high density lipoprotein; hs CRP: high sensitive C-reactive protein; HST = human smoking topography; LDL: low density lipoprotein; mCC = menthol conventional cigarette(s); MCEQ = Modified Cigarette Evaluation Questionnaire; MNWS = Minnesota Nicotine Withdrawal Scale; SAE = serious adverse event; s-ICAM-1: soluble inter-cellular Molecule 1; TC: total cholesterol; TG = triglycerides; THS = tobacco heating system; QSU = Questionnaire of Smoking Urges; WBC = white blood cell count.

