COHb blood sampling	Days -1 to 4 Morning sample on Day 5 Day 5 other samples Day 30 and Day 60 Day 90	08:00 PM to 09:30 PM Within 15 minutes prior to product use (for THS 2.2 Menthol and mCC arms) or between 08:00 AM and 09:30 AM (SA arm) Between 12:00 PM and 01:30 PM, 04:00 PM and 05:30 PM, and 08:00 PM and 09:30 PM Irrespective of product use between 10:00 AM and 11:30 AM. Irrespective of product use between 10:00 AM and 12:30 AM.
HST Questionnaire	Day 0 Day 4, Day 30, Day 60 and Day 90 for all subjects in the THS 2.2 Menthol and mCC arms	08:00 PM-11:00 PM 08:00 PM-09:30 PM
HST Recording	Day 0 Day 1 and Day 4 for all subjects in the THS 2.2 Menthol and mCC arms smoking compatible mCC Day 30, Day 60 and Day 90 for all subjects in the THS 2.2 Menthol and mCC arms smoking compatible mCC	06:30 AM-11:00 PM 06:30 AM-11:00 PM Start time: 08:30 AM to 09:30 AM. End time: 12:30 PM to 01:30 PM. 4-hour recordings ± 15 min
Ambulatory Visit	Day 30 Visit, Day 60 Visit and Day 90 Visit	± 3 days.

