12.6.1 Primary Analyses

12.6.1.1 Analysis of Biomarkers of Exposure for Primary Objectives

The BoExp (COHb in blood and urinary concentrations of MHBMA, 3-HPMA, S-PMA and Total NNAL) used for the primary analysis will be described as detailed in Section 12.1.3 “Descriptive Statistics”. The listing of the COHb data will have a flag for whether a subject’s COHb was <2%.

The baseline is as defined in Section 12.1.4 “Definitions for Statistical Data Analysis”.

The primary endpoints will be log-transformed (base_e) prior to analysis. The analysis will compare the evening COHb level (20:00-21:30) at Day 5; and urinary concentrations of MHBMA, 3-HPMA and S-PMA adjusted for creatinine on Day 5 and urinary concentrations of Total NNAL adjusted for creatinine on Day 90 Visit between the THS 2.2 Menthol and mCC arms for the PP Set. An analysis of covariance (ANCOVA) (Snedecor and Cochran 1982) model will be used with terms for the log-transformed baseline value, sex, average daily mCC consumption over the last 4 weeks as reported during screening and randomization arm.

The SAS code to be used for the THS 2.2 Menthol and mCC data is shown below:

```
Proc glm data=_data_ ;
  Class randomization_arm sex cigarette_cons;
  Model log_biomarker = log_baseline sex cigarette_cons
    randomization_arm;
  Lsmean randomization_arm / pdiff =control('mCC') alpha=0.05 cl;
  Run;
```

The least squares (LS) means and estimate of the difference and the 95% CI will be back-transformed. The geometric LS means for each randomization arm along with the ratio (THS 2.2 Menthol : mCC), two-sided 95% CI and one-sided p-value will be presented in the tables. THS 2.2 Menthol : CC effects will be graphed in a forest plot.

All figures, summaries and analyses will be performed on the PP Set. Additional descriptive statistics will be provided within the secondary analysis.

The data will be presented in the below outputs:

TFL number	Title
FIGURES	
15.1.1.1	Forest Plots of Statistical Analysis of Biomarkers of Exposure for Primary Objective – PP Set
15.1.1.2	Biomarker of Exposure for Primary Objective Arithmetic Mean and 95% CI for Percent Change from Baseline – PP Set
TABLES	
15.2.3.1.1	Analysis of COHb, MHBMA, 3-HPMA, S-PMA and Total NNAL on Day 5/90 Visit for THS 2.2 Menthol versus mCC for the Primary Objective – PP Set
15.2.4.1.1	Descriptive Statistics of Blood COHb (%) – PP Set
15.2.4.1.1.1	Descriptive Statistics of Blood COHb (%) by Sex – PP Set

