12.6.2.2 Nicotine and Cotinine Concentrations

The concentrations of nicotine and cotinine will be listed and summarized. During confinement, the evening concentration levels at 08:00 PM is considered. Baseline is the assessment at 08:00 PM to 09:30 PM on Day 0. Line graphs of the nicotine and cotinine concentration profiles across all study days showing mean and 95% CI of percent change from baseline will also be produced.

Nicotine and cotinine concentrations at each post-baseline timepoint will be analysed in the log space using an ANCOVA model with terms for log-transformed baseline concentration, sex, average daily mCC consumption over the last 4 weeks as reported during screening, time point, product, and the interaction term between time point and product. No adjustment will be made for multiple comparisons.

The SAS code described in Section 12.6.1.3 "Sensitivity Analysis" will be used for the analysis of nicotine and cotinine.

Geometric LS means for each product along with the ratio (THS 2.2 Menthol : mCC) and 95% CI will be presented in the tables.

All figures, summaries and analyses will be performed on the PP Set and FAS by randomization arm.

The data will be presented in the below outputs:

TFL number	Title
FIGURES	
15.1.2.1.1	Plasma Nicotine and Cotinine Profile (ng/mL) over the 90 Days Arithmetic Mean and 95% CI for Percent change from baseline – PP Set

TFL number	Title
15.1.2.1.2	Plasma Nicotine and Cotinine Profile (ng/mL) over the 90 Days Arithmetic Mean and 95% CI for Percent change from baseline – FAS
TABLES	
15.2.4.19.1	Descriptive Statistics of Plasma Nicotine and Cotinine Concentrations (ng/mL) – PP Set
15.2.4.19.2	Descriptive Statistics of Plasma Nicotine and Cotinine Concentrations (ng/mL) – FAS
15.2.4.20.1	Analysis of Plasma Nicotine and Cotinine Concentrations (ng/mL) over the 90 Days – PP Set
15.2.4.20.2	Analysis of Plasma Nicotine and Cotinine Concentrations (ng/mL) over the 90 Days – FAS
LISTINGS	
15.3.3.3	Listing of Plasma Nicotine and Cotinine Concentrations

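### Blood COHb and plasma nicotine/cotinine are read in the evening at baseline and in confinement but in the morning at Day 30/60/90, so percent change from baseline and the joined 90-day profile mix time of day with exposure

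*SAP*

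**What the plan says.** **Baseline and confinement.** For COHb, Protocol 7.5.1.1 states: "On Day -1 to Day 4: one blood sample will be collected in the evening between 8:00 PM-09:30 PM". Day 5 has four COHb samples, and SAP 12.6.1.1 picks the last: "The analysis will compare the evening COHb level (20:00-21:30) at Day 5". Under the general baseline rule in SAP 12.1.4 (last assessment before first randomized product use), the COHb baseline is the Day 0 evening sample. For nicotine and cotinine, SAP 12.6.2.2 uses the evening level in confinement and adds: "Baseline is the assessment at 08:00 PM to 09:30 PM on Day 0".

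**Ambulatory visits.** For COHb at Day 30 and Day 60, SAP Table 18 (section 11.1.3) gives: "Irrespective of product use between 10:00 AM and 11:30 AM". For Day 90 it prints: "Irrespective of product use between 10:00 AM and 12:30 AM". Protocol Table 18 ends the Day 90 window at 12:30 PM, so the SAP entry needs reconciling. SAP Table 18 has no ambulatory window for nicotine/cotinine. Protocol Tables 17 and 18 place that single draw in the same morning slots as COHb.

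**Reporting.** SAP 12.1.3 summarises blood biomarkers over time as levels and as percent change from baseline. SAP 12.6.2.2 plots nicotine and cotinine percent change across all study days. SAP 12.6.2 repeats the COHb model at Day 90. None of these sections mentions the change in sampling time.

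**The concern.** COHb and plasma nicotine should accumulate over a smoking day, so a mid-morning level and an evening level differ in a person whose smoking has not changed. Dividing a morning value by an evening baseline builds a step between Day 5 and Day 30 into every smoking arm. Where a marker also has a non-smoking background, the step is larger in mCC than in THS, and the COHb ratio moves a little towards 1.

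This bears on secondary objectives 3 and 4, which cover the whole exposure period, and on the contrast drawn in Protocol 4.2 between maximum reduction in confinement and real-world use afterwards. A fall in mCC smokers could be read as reduced smoking, and a rise in the COHb ratio as fading effect or dual use.

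The SAP already treats clock time as material. Its carry-forward rule (12.1.5) replaces a missing Day 5 evening COHb with the Day 4 evening value even when other Day 5 samples exist.

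**Working it through.** The plan gives no figure for this effect. Its COHb assumptions (SAP Tables 11 and 13) do reproduce the stated joint power for a 50% reduction: 0.943 and 0.982 against 94% and 98%, taking the product over the five endpoints of two-sample power on the log scale with SD = √ln(1+CV²). Power is not affected by this point.

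**Inputs from the documents**
- Evening window 20:00-21:30, midpoint 20:45. Day 30/60 window 10:00-11:30, midpoint 10:45.
- Confinement product use from 06:30 to 23:00.
- COHb THS/mCC = 0.40 and THS/SA = 2.10 (SAP Table 11), so background/mCC = 0.40/2.10 = 0.19.
- Second assumption set: COHb THS/mCC = 0.44 (SAP Table 13).
- Half-life: Protocol 4.2 says only that the Day 5 primary biomarkers average 24 h or less.

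**Assumptions, not in the documents**
- Even smoking from 06:30 or 07:30 to 23:00, with the same pattern on every day.
- First-order loss, with a half-life of 2-6 h as the main range.

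**Step 1: morning/evening ratio r of the smoking-related part.** Let L be the length of the smoking day (16.5 or 15.5 h), k = ln2/half-life, and t the hours since smoking starts. In units of intake rate/k, at steady state:

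C(t) = C₀e^(−kt) + 1 − e^(−kt), with C₀ = (1 − e^(−kL))·e^(−k(24−L)) / (1 − e^(−24k)).

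Example, half-life 4 h, start 06:30: C₀ = 0.9427 × 0.2726 / 0.9844 = 0.261. At 10:45 (t = 4.25), C = 0.261 × 0.479 + 0.521 = 0.646. At 20:45 (t = 14.25), C = 0.261 × 0.085 + 0.915 = 0.937. So r = 0.69.

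| Half-life (h) | r, start 06:30 | r, start 07:30 |
|---|---|---|
| 2 | 0.79 | 0.70 |
| 3 | 0.71 | 0.62 |
| 4 | 0.69 | 0.60 |
| 5 | 0.69 | 0.61 |
| 6 | 0.71 | 0.63 |

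**Step 2: total COHb, with mCC evening = 1.**
- mCC morning = 0.19 + 0.81r. At r = 0.79 this is 0.83, a 17% fall. At r = 0.60 it is 0.68, a 32% fall.
- THS morning = 0.19 + 0.21r = 0.36 or 0.32, against 0.40 in the evening, a fall of 11% or 21%.
- THS:mCC = (0.19 + 0.21r)/(0.19 + 0.81r) = 0.43 or 0.47, against a true 0.40.
- Second set, carrying over the 0.19 background: (0.19 + 0.25r)/(0.19 + 0.81r) = 0.47 or 0.50, against a true 0.44.

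**Step 3: wider half-lives.** With a 06:30 start, half-lives of 1-24 h and draws from 10:00 to 12:30, mCC COHb is 1-29% below the evening value. A ratio of 0.40 reads 0.40-0.46.

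**Step 4: nicotine and cotinine.** With no background, the same grid gives morning levels 2-36% below evening. If both arms share the same kinetics the between-arm ratio does not move, so only the within-arm percent change is affected. The documents give no half-life for either marker.

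**The case against.** Much of the opposing case stands.

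- **The primary analysis is untouched.** Day 5 COHb is an evening value with an evening baseline. At each ambulatory visit all arms are sampled in the same window, so the Day 90 between-arm contrast is valid. No Day 5 versus Day 90 test is planned.
- **The size rests on outside kinetics.** Smoking before 08:00 on visit days is unrestricted, and nothing limits night smoking at home. Either would shrink the effect.
- **Other data separate time of day from setting.** Day 5 includes a 12:00-13:30 COHb sample and a two-hourly nicotine/cotinine profile. Exhaled CO is measured four times a day from Day -1. Urinary nicotine equivalents over 24 h do not depend on a draw time. A reader might infer that setting and clock time cannot be disentangled; these samples show that they largely can.
- **A morning draw is defensible.** Subjects check in at about 08:00, so a morning sample carries more of the use at home that the ambulatory period is meant to show.
- **Topography does not distinguish the ambulatory draw from baseline.** The device is also used on Day 0, so the evening baseline is itself a recording-day value.

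What remains is that the SAP, followed as written, divides morning values by an evening baseline and runs the two together without comment, although better-matched samples exist.

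**Conclusion.** The point holds for within-arm change from baseline and for comparing Day 5 with Day 30/60/90. Under the stated smoking pattern, a half-life of 2-6 h and a background of 0.19, unchanged mCC smokers would show COHb about 17-32% lower at 10:45, and a ratio of 0.40 would read about 0.43-0.47. Over half-lives of 1-24 h the mCC fall runs from about 1% to about 30%, and the ratio drift can be near nil. The direction is the same throughout; the size is uncertain.

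Two stronger readings are not supported. A reader might infer that the artefact would carry ambulatory COHb across the 50% line. That criterion applies to COHb at Day 5 only (SAP 5.5.2). Ratios up to about 0.53 also need the whole THS level of 0.40 to be a fixed floor: 0.40/(0.40 + 0.60 × 0.60) = 0.53. The THS/SA ratio of 2.10 puts the floor at 0.19. A reader might also infer that the Day 90 comparison between arms is biased; it is not.

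The change is worth making because it removes an avoidable misreading at small cost. It does not bear on the study's success criterion.

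**What to change.** Change the SAP only.

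1. In 12.1.3, 12.6.1.1/12.6.2 and 12.6.2.2, report Day 30/60/90 COHb and nicotine/cotinine as levels and between-arm ratios, not as percent change from the evening baseline.
2. In the COHb and nicotine/cotinine figures, break the line between Day 5 and Day 30 and label the sampling times.
3. For confinement versus ambulatory, set ambulatory COHb beside the existing Day 5 12:00-13:30 sample. Set ambulatory nicotine/cotinine beside the Day 5 profile sample nearest in clock time (about T0+4 h). This is possible in the THS and mCC arms only, because the SA arm has no Day 5 profile.
4. Reconcile the Day 90 window in SAP Table 18 with the protocol's 12:30 PM. The CO breath test row has the same entry.

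**Cost.** A few tables and figures change; no new sample is needed and the primary analysis stays as it is. The midday match is approximate: in the model above, at half-lives of 2-6 h, its ratio lies within about 0.02 of the ratio at 11:15, the middle of the Day 90 window.

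Moving the ambulatory draw to the evening is not recommended. Subjects stay on site overnight ("will remain overnight on site until respectively Day 31, Day 61, and Day 91"), so it would be feasible, but after about 12 hours on site it would capture less of the use before check-in. It is probably also too late: the protocol expected the study to end on 31 August 2014, and SAP version 2.0 is dated 07 November 2014.

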12 PLANNED STATISTICAL METHODS

12.1 General Considerations

Data analysis will be performed using SAS[®] Version 9.3.

Data listings will be provided for all data collected as defined in the protocol, ordered by randomization arm and subject, Day, Visit and time point (if applicable), unless otherwise stated. Summary statistics and statistical analysis will only be presented for data where detailed in this SAP. All unscheduled assessments will be included in the listings.

12.1.1 Stratified Presentation

The following summaries will be produced by randomization arm, stratified by sex (male vs. female) and mCC consumption (10-19 mCC/day vs. >19 mCC/day) for the PP set at period 1 and 4:

- Demographics and Baseline Characteristics
- COHb, and MHBMA, 3-HPMA, S-PMA and total NNAL adjusted for creatinine.
- Product use

Summaries of data by product use categories will be produced for the product use time periods 1 to 4 (see Table 20), as appropriate.

Summaries of safety data will be provided stratified by pre-randomization and randomized period (see Table 20).

All endpoints will be summarized stratified by time point as appropriate.

12.1.2 Subgroup Analyses

No subgroup analyses will be performed in this study.

12.1.3 Descriptive Statistics

For continuous data, summary statistics will include the number of subjects (n), the number and percent of subjects with missing data, the arithmetic mean, arithmetic standard deviation (SD), 95% confidence interval (95% CI), median, first and third quartiles, minimum and maximum; for log-normal data the geometric mean, geometric 95% confidence interval and geometric coefficient of variation (CV) will also be presented instead of the SD and 95% CI of the arithmetic mean. For categorical data, frequency counts and percentages will be presented. Data listings will include all subject level data collected unless otherwise specified.

Unless otherwise specified, data described over time will be reported for the 2 – 4 periods (see Table 20).

Data for early termination will be summarized at the end of the corresponding period (1-4). Data for early termination collected during an unplanned ambulatory visit will be handled as specified in Section 12.1.6 “Handling of Unplanned Data”.

Urinary BoExp Summaries

In general, urinary BoExp will be described over time as follows:

- Summary of concentration values adjusted for creatinine, and their percent change from baseline. Line graphs will be produced for arithmetic means of creatinine adjusted concentration (and 95% CI of the mean) for the percent change from baseline over all timepoints.
- Summary of quantity excreted over 24-hours values.

In general, BoExp measured in blood or breath tests will be described with summaries of the levels over time and levels expressed as percent change from baseline. BoExp levels will also be presented with line graphs.

Summaries and graphs will be produced for the FAS and PP Set. All derived variables will be listed together with the raw BoExp levels.

Safety Summaries

In general, summaries for the Safety and Full Safety populations will be produced by randomization arm, separately for the following periods:

- Pre-Randomization, including safety data collected until randomization. Only for this period, the Safety population includes any subjects who tested the product but were not randomized and these subjects will be reported in a separate “Product Test Only” group.
- Randomized period, including Baseline and all post-Baseline data.

The following product labels will be used throughout the TFLs (Table 19):

Table 19: Product Labels

Product	Format used in TFLs	Order in TFLs
Tobacco Heating System 2.2 Menthol	THSm2.2	1
Menthol conventional cigarettes	mCC	2
Smoking abstinence	SA	3

The following stratification labels (Table 20) for the TFLs will be used:

Table 20: Stratification Labels

Stratification Factor	Label (Definition)
Product preference (which product the subject would prefer to be randomized to).	THSm2.2 (THS 2.2 Menthol)
	mCC
	SA
	NP (No preference)

Sex	Male Female
Daily mCC consumption	10-19 >19
Safety Time Periods	Pre-Randomization period ([Product trial – Randomization]) Randomized period Confinement ([Day 1-Day 6 confinement]) Ambulatory ([Day 6 ambulatory-Day 90 Visit]) Safety Follow-up ([Day 90 Visit – End of Study])
Product Use Time Periods	Period 1 ([Day 1-Day 6 confinement]) Period 2 ([Day 6 ambulatory-Day 30 Visit]) Period 3 (]Day 30 Visit-Day 60 Visit]) Period 4 (]Day 60 Visit-Day 90 Visit])
Product Use Categories for mCC arm	CC Only (Exclusively CC) CC Dual (Use of other products)
Product Use Categories for SA arm	Abstinent Predominantly Abstinent Not Abstinent
General Product Use Categories for THS 2.2 Menthol arm	THS 2.2 [70-100%] Dual]30-70%[CC [0-30%]
Detailed Product Use Categories for THS 2.2 Menthol	Primarily THS 2.2 (]95-100%) Predominantly THS 2.2 ([70-95%]) Dual Mostly THS 2.2 (]60-70%) Dual Balanced ([40-60%]) Dual Mostly CC (]30-40%[) Predominantly CC ([5-30%]) Primarily CC ([0-5%])

Unless otherwise defined, the text in brackets () will be used to define the labels in the TFL footnotes

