5.1.3 Removal of Subjects from the Study

Subjects will be informed that they are free to withdraw from the study at any time. Subjects should be questioned for the reason of premature withdrawal, although they are not obliged to disclose it. This needs to be fully documented in the Source Document and electronic Case Report Form (eCRF).

When a subject withdraws or is removed from the study, the whole safety examination procedure planned on Day 6 must be performed as soon as possible after the time of withdrawal unless the subject has withdrawn their informed consent to do so. After the time of withdrawal, the subject will enter into the 28-day period of safety follow-up. Subjects withdrawn or removed from the study cannot re-enter the study.

Subjects must be withdrawn from the study for any of the following reasons:

- Withdrawal of informed consent.
- Any AE or condition (including clinically relevant changes in a laboratory parameter), which at the discretion of the Investigator.
- Positive pregnancy testing (any invasive procedures, including the drawing of blood MUST NOT be performed after diagnosis of pregnancy, see Section 8.5).
- The Sponsor or Principal Investigator terminates the study. If the Sponsor or the Principal Investigator decide to prematurely terminate the study, the subject will be promptly informed and will follow the end of study procedures as described in Section 9.5. The head of the medical institution will report this fact and the reason in writing to the IRB. If a study site is discontinued for non-compliance with ICH/GCP, subjects enrolled at that

Data and information contained in this document are considered to constitute trade secrets and confidential commercial information, and the legal protections provided to such trade secrets and confidential information are hereby claimed under the provisions of applicable law. No part of this document may be publicly disclosed

without the written consent of Philip Morris Products S.A.

site will not be included in the primary study populations, and therefore enrolment will be extended to meet the sample size requirement.

- Withdrawal is considered to be in the best interest of the subject or the other subjects.
- The subject wish to quit smoking (this is applicable for all subjects during screening to the baseline period and for subjects allocated to THS 2.2 Menthol or mCC arms during the exposure period).

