9.5 Early Termination Procedures

The safety assessments as described on Day 6 will be performed as early termination procedures (see Section 9.2.4).

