12.1.6 Handling of Unplanned Data

Unscheduled post-product use readings will be excluded from the summary statistics. Unscheduled readings will be labelled as unscheduled in the listings and mapped to the relative study day using the date of the study day until midnight.

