12.6.4.2.4 Laboratory Abnormalities

The shift in toxicity grades from Baseline to worst grade recorded while in the Randomized period will be presented in tables for the clinical chemistry, hematology and urinalysis parameters. Details related to the toxicity grading of laboratory abnormalities are available in Section 12.6.4.3 “Clinical laboratory Evaluation”.

The data will be presented in the below outputs:

TFL number	Title
TABLES	
15.2.6.16.1	Summary of Clinical Chemistry Parameters – Safety Population
15.2.6.16.2	Summary of Clinical Chemistry Parameters – Full Safety Population
15.2.6.17.1	Summary of Hematology Parameters – Safety Population
15.2.6.17.2	Summary of Hematology Parameters – Full Safety Population
15.2.6.18.1	Summary of Urinalysis Parameters – Safety Population
15.2.6.18.2	Summary of Urinalysis Parameters – Full Safety Population

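### Exit safety readings from unplanned ambulatory visits are left out of the by-visit safety summaries, and the SAP contradicts itself on whether they count in the laboratory worst-grade shift

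*SAP*

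**What the plan says.** **Exit examination.** Protocol 5.1.3 states that when a subject withdraws or is removed, "the whole safety examination procedure planned on Day 6 must be performed as soon as possible after the time of withdrawal", unless consent to it has been withdrawn. Protocol 9.5 agrees: "The safety assessments as described on Day 6 will be performed as early termination procedures". Protocol 8.6 has a parallel rule for subjects withdrawn because of an adverse event. The Day 6 schedule (Protocol Table 16) includes the safety laboratory panel, ECG, vital signs and spirometry.

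**Summaries.** SAP 12.1.3 gives a general rule, "Data for early termination will be summarized at the end of the corresponding period (1-4", followed at once by an exception: "Data for early termination collected during an unplanned ambulatory visit will be handled as specified in Section 12.1.6". Section 12.1.6 then says "Unscheduled post-product use readings will be excluded from the summary statistics" and "Unscheduled readings will be labelled as unscheduled in the listings". SAP 12.1 confirms the listings: "All unscheduled assessments will be included in the listings".

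**Provisions pointing the other way.** SAP 12.6.4.2.4 says "The shift in toxicity grades from Baseline to worst grade recorded while in the Randomized period will be presented in tables". The safety part of SAP 12.1.3 describes the randomized period as covering baseline and everything recorded after it.

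**The concern.** The exception covers the usual case in the longer phase of the study. A subject who leaves during the 85-day ambulatory phase and is examined promptly will often be seen at a visit that was not planned. The reading is then listed but not summarized. A subject who leaves in confinement and has the same examination is summarized.

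Exit readings are plausibly informative, because Protocol 5.1.3 names adverse events and clinically relevant laboratory changes among the conditions for withdrawal. The exclusion may also fall unevenly across arms. During exposure, a wish to quit smoking leads to withdrawal in the THS 2.2 Menthol and mCC arms but not in the SA arm.

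The laboratory worst-grade shift is a separate problem. Such a table exists to capture the most abnormal value whenever it occurred. Two parts of the SAP give the programmer opposite instructions for it. The conflict extends beyond early termination, because 12.1.6 applies to any unscheduled reading after product use.

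**Working it through.** The plan gives no figure on this point, so the check is mainly a tracing of the text.

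**Step 1: where each exit reading goes.**

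| Exit examination | Governing text | Result |
|---|---|---|
| In confinement | SAP 12.1.3, general rule | Summarized at end of period 1 |
| At a planned ambulatory visit | SAP 12.1.3, general rule | Summarized at end of periods 2 to 4 |
| At an unplanned ambulatory visit | SAP 12.1.3 exception, then 12.1.6 | Excluded from summary statistics, listed |
| Laboratory worst grade, unplanned visit | 12.1.6 against 12.6.4.2.4 and the safety part of 12.1.3 | Unresolved |
| Finding recorded as an adverse event | SAP 12.6.4.2 | In the AE tables |

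**Step 2: does another rule bring the readings back?** None was found for the by-visit tables.

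- Laboratory (SAP 12.6.4.3) and ECG (12.6.4.4.5) are summarized at baseline, Day 6 and the Day 30, 60 and 90 visits. Vital signs (12.6.4.4.3) are summarized by study day. Spirometry (12.6.4.4.4) is summarized at baseline, Day 6 and the Day 90 visit. None has an early-termination row.
- Last observation carried forward is specified in SAP 12.1.5 for biomarkers of exposure. There is no counterpart for safety parameters.
- Protocol 12.6.5 promises shift tables for ECG, physical examination and laboratory parameters without excluding exit readings. SAP section 9, which lists changes from the protocol, mentions no such exclusion.

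**Step 3: how much of the ambulatory phase lies outside planned visits?** Inputs: discharge from confinement on Day 6, end of exposure on Day 90, and visits at Days 30, 60 and 90 with a window of ±3 days (SAP Table 18).

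- Days 7 to 90: 90 − 7 + 1 = 84 days.
- Days inside a window: 27–33 (7), 57–63 (7) and 87–90 (4), so 7 + 7 + 4 = 18.
- Share outside: (84 − 18)/84 = 66/84 = 78.6%.

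Each visit spans two days, so a visit starting on Day 33 ends on Day 34. Adding Days 34 and 64 gives 20 days inside and (84 − 20)/84 = 64/84 = 76.2% outside. These are shares of calendar time. They become shares of exit examinations only if withdrawals, and the examinations that follow, are spread evenly over the phase.

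**The case against.** There is a substantial case that little is lost.

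- **Scope of the exclusion.** SAP 12.1.3 uses the term summary statistics for continuous data and deals separately with counts and percentages for categorical data. On that reading, 12.1.6 removes unscheduled values from means and medians but not from shift or worst-grade counts. This is a fair reading but not the only one, since SAP 12.1 uses the same term without that restriction.
- **Specific over general.** Section 12.6.4.2.4 is specific to the worst-grade table and could be held to prevail. The SAP states no precedence, so this supports calling the text contradictory. It does not settle the matter.
- **The AE route.** Protocol 8.4.1 requires Grade 2 and higher laboratory values to be reported as, or linked to, an adverse event or concomitant disease. Protocol 12.6.5 makes adverse events the primary safety assessment. This stands, but as a partial safeguard: Grade 1 values and other test results become adverse events only if judged clinically relevant (Protocol 8.4.1, 8.4.2), and AE counts do not replace change-from-baseline and shift tables.
- **The triggering value.** Scheduled ambulatory laboratory panels and ECGs occur only at the three visits. A laboratory change that prompts withdrawal may well be found there and would already be in the visit table. This weakens the even-spread assumption most for subjects withdrawn for laboratory reasons.
- **By-visit means.** Keeping off-schedule values out of nominal-visit means is sound practice, and the fix preserves it.

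A reader might infer that exit readings vanish from every summary, or that the safety tables describe only subjects who stayed. The documents support neither. The worst-grade table is contradictory rather than clearly closed to these readings, and a withdrawn subject's earlier scheduled readings remain in the tables.

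**Conclusion.** The point holds within limits. A stated rule, not a missing detail, leaves exit laboratory, ECG, vital-sign and spirometry values from unplanned ambulatory visits out of the by-visit summaries. For the laboratory worst-grade shift the SAP contradicts itself.

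The 79% (76% if both days of each visit are counted) rests on evenly spread withdrawals. It measures opportunity, not expected loss. The documents give no rate of ambulatory withdrawal for safety reasons, so the number of affected subjects cannot be estimated.

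It would also go too far to say that the rule removes the readings of subjects withdrawn for safety. It applies to early termination for any reason, and some subjects will have declined the examination. The primary biomarker analyses are untouched. What is at stake is the completeness and reproducibility of the safety tables.

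**What to change.** Reconcile SAP 12.1.3, 12.1.6 and 12.6.4.2.4 as follows:

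1. State that worst-grade, shift and clinically-significant-abnormality tables use all post-baseline readings, including unscheduled and early-termination ones.
2. Show early-termination safety readings in a separate early-termination row of the laboratory, ECG, vital-sign and spirometry tables, by arm.
3. Limit the 12.1.6 exclusion to by-visit statistics at nominal visits, and replace the cross-reference in 12.1.3 accordingly. Do not map off-schedule exit values into those visits: a Day 36 reading, for example, should not be averaged with Day 60 values.

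The cost is SAP wording, one extra row or flag in the safety tables and minor programming. No new data are needed.
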